STUDY PROTOCOL (20.12.2021)

Title of Study:

Evaluation of the Effect of Muscle Activity on Subjective Tinnitus in Temporomandibular Disorders

Title, name, area of expertise and place of duty of principal investigator:

[name], Department of Oral and Maxillofacial Surgery; Kütahya University of Health Sciences Faculty of Dentistry

Title, names, fields of expertise and place of duty of all researchers who will be involved in the research:

[name], Physical Medicine and Rehabilitation; Kütahya University of Health Sciences Faculty of Medicine

[name], Department of Oral and Maxillofacial Surgery; Kütahya University of Health Sciences Faculty of Dentistry

[name], Department of Periodontology; Kütahya University of Health Sciences Faculty of Dentistry

[name], Department of Prosthodontics; Kütahya University of Health Sciences Faculty of Dentistry

[name], Department of Prosthodontics; Kütahya University of Health Sciences Faculty of Dentistry

[name]; Physical Medicine and Rehabilitation; Kütahya University of Health Sciences Faculty of Medicine

[name], Department of Oral and Maxillofacial Surgery; Kütahya University of Health Sciences Faculty of Dentistry

Where the research will be conducted:

Kütahya University of Health Sciences Faculty of Dentistry

PHASE OF THE RESEARCH AND TYPE	PHASE 1	
	PHASE 2	
	PHASE 3	
	PHASE 4	
	observational drug study	
	Medical device clinical research	
	Performance evaluation studies with in vitro medical diagnostic devices	
	Non-drug clinical research	
	If other, specify:	

The planned date range of the research: 25.12.2021-15.11.2022

The hypothesis of the research:

$\mu = 1$ hypothesis: Temporomandibular disorder accompanied by subjective tinnitus and treatment of bruxism with an occlusal splint; It has an effect on the decrease in the levels of tinnitus, bruxism and temporomandibular disorder.

$\mu = 0$ hypothesis: Temporomandibular disorder accompanied by subjective tinnitus and treatment of bruxism with occlusal splint; It has no effect on the decrease in the levels of tinnitus, bruxism and temporomandibular disorder.

Introduction-Purpose Section:

Temporomandibular disorders; is a general term describing disorders of the masticatory muscles, temporomandibular ligaments, and temporomandibular joint (TMJ). The most common symptoms of these disorders are pain in the preauricular region and masticatory muscles, limitation/irregularity in joint movements and sounds coming from the joint. Additional symptoms include; headache, tinnitus, dizziness, hearing loss, sleep disturbance, and chronic fatigue. Bruxism is one of the most common predisposing factors that cause temporomandibular disorders.

Bruxism is a repetitive jaw-muscle activity that occurs with mandible movement characterized by clenching and/or grinding of the teeth. Bruxism can occur during the day or night while sleeping or awake. While clenching is more prominent in diurnal bruxism, grinding is seen in addition to clenching in nocturnal bruxism. Factors such as stress, occlusal irregularities, allergies, and sleep quality are discussed in its etiology. Treatment includes botulinum toxin injection and/or occlusal splint.

Occlusal splints are one of the most common and first-choice treatment modalities in patients with TMD and bruxism, as they are a non-invasive and easily accessible treatment option. These splints are used to correct the static and dynamic effects of the stomatognathic system. With the occlusal splint, equal and balanced occlusal contact is achieved without permanently changing the resting position of the mandible and/or dental occlusion. It is usually in the form of a dental retainer or removable prosthesis made of hard acrylic. The most commonly used type of occlusal splint is the Michigan type bite splint. This splint is mostly used in the maxilla. The main purpose of this appliance is to separate the occlusion, put the condyle in a centric position, relax the chewing muscles and prevent further tooth wear due to parafunctional activity. The main feature of the Michigan type bite splint is that it can easily provide centric and canine-protected occlusion.

Tinnitus is defined as the perception of sounds in one's ears or inside the head without any acoustic stimulus. Sounds can be perceived in the ear or in the head. Microtrauma associated with repetitive activities, such as bruxism, is considered a risk factor for the onset and persistence of muscle pain and may be directly related to the symptom of tinnitus. Hyperactivity in the masticatory muscles as a result of bruxism may affect the tensor tympani muscle and the auditory system and trigger tinnitus. ¹ Ramirez et al. reported that the tensor veli palatini muscle

lost its function in patients with bruxism, and the position of the tympanic membrane and malleus could change due to its union with the tensor tympani muscle.² Therefore, they reported that velopharyngeal, neck and facial movements have an important role in the symptoms of otic-temporomandibular disorder.² In the study by Camparis et al., it was found that the frequency of tinnitus is high in patients with sleep bruxism and chronic myofascial pain; At the same time, it was reported that the number of painful areas on palpation in the chewing and cervical muscles and the absence of teeth were more common in the tinnitus group, and the tinnitus frequency was higher in patients with sleep bruxism.³ In the study of Kuttilla et al., it was reported that the pain in the chewing muscles in patients with tinnitus was higher than the control group.⁴ Bernhardt et al. reported that tinnitus patients had more muscle and TMJ pain than the control group.⁵ According to the positive correlation between bruxism and tinnitus; Since oral parafunctions trigger both conscious and unconscious jaw movements, it is thought that abnormal activity of the masticatory muscles and jaw joint may trigger a more intense tinnitus sensation.

In this study, we also; We aimed to treat patients with temporomandibular disorder accompanied by tinnitus with the use of occlusal splint, which is minimally invasive and the most preferred method. At the same time, we aimed to compare the data between the use of superficial EMG and the electrical activity of the masseter muscle, which is the main chewing

muscle, and temporomandibular disorder, bruxism, subjective tinnitus, and to elucidate the etiology of subjective tinnitus, which is the subject of discussion in the literature. The use of an occlusal splint is one of the most effective methods in the management of temporomandibular joint disorders and in reducing symptoms such as joint/muscle pain and limitation in mouth opening. With this treatment method, simultaneous treatment of subjective tinnitus seen with the temporomandibular joint is aimed.

Material-Methods Section:

The study will be conducted with patients who routinely apply to Kütahya Health Sciences University Faculty of Dentistry. 70 patients with temporomandibular disease accompanied by tinnitus and bruxism will be included in the study. Demographic data such as age, gender, and systemic disease, drug and trauma history data will be collected.

TMD findings of the patients will be classified according to Wilkes classification. The Wilkes classification is as follows:

1. Stage 1 (early period): No pain or limitation of jaw movements, only reciprocal click during or after chewing. Mild anterior disc displacement in radiological evaluation.
2. Stage 2 (early/intermediate): Mild to moderate pain with reciprocal clicking and periodic locking. Change in disc position.
3. Stage 3 (intermediate): Joint tenderness with frequent pain. Ongoing crash. On the radiological image, changes in disc position and deformation with adhesions.
4. Stage 4 (intermediate/late): Chronic pain that gets worse from time to time and limitation in jaw movements. Change in the shape and position of the disc and the shape of the condyle. Multiple adhesions with hard tissue changes.
5. Stage 5 (late stage): pain that occurs from time to time with crepitation.

Bruxism data (time of onset, whether it is felt during the day/night, fatigue, difficulty in opening the mouth in the morning, stressful period) are questioned and examination findings (disc displacement, masseter hypertrophy on inspection, linea alba, attrition of teeth, fractures in restorations and teeth, muscle and joint pain), facial asymmetry, mouth opening) will be recorded. The characteristics of tinnitus (objective/subjective, duration, in which ear, increasing and decreasing factors, type) and hearing loss, vertigo will be questioned.

Patients will be divided into two groups. Group I will consist of Wilkes Stage 1-2 patients with temporomandibular intra-articular disorder. Group II will consist of patients with both Wilkes Stage 1-2 temporomandibular intra-articular disorder and bruxism.

In order to measure the muscle strength of the patients before the treatment, in order to reach the chewing muscles easily and to minimize the patient's discomfort, EMG containing right-left M. Masseters will be taken. The analog EMG signal will be amplified using a differential amplifier with a high common-mode rejection ratio (bandwidth 5 KHz, peak-to-peak input range 200 μ V). The average of the signals is over 500 ms. (Micromed, Italy)
Superficial EMG will be taken following the following protocol:

- To reduce skin impedance, the skin will be cleaned before electrode placement and recordings will be made after 5-6 minutes.
- Superficial electrodes will be placed on the right and left masseter muscles, with the upper pole of the electrode parallel to the intersection between the tragus-labial commissura and the exocantion-gonion lines. The grounding electrode will be placed in the forehead area.
- For all tests, patients will be seated with their head unsupported and asked to maintain a natural upright position.
- To avoid any effects of fatigue, a rest period of at least 3 minutes will be allowed between tests. The average EMG potential for each of the muscles will be set to 100%.
- To standardize EMG potentials, two 10 mm thick cotton rolls will be placed on each subject's mandibular first and second molars, and maximum voluntary clamping of 5 seconds will be recorded. For 5 seconds, the patient will be encouraged to maintain the same level of contraction. EMG data analysis for all tests, the best 3-s period (the one with the most stable signal) will be automatically selected by the software and used for all subsequent analysis.
- Electromyographic activity will then be recorded with a maximum voluntary squeeze at the intercuspal position; The patient will be invited to squeeze as hard as possible and maintain the same level of contraction for 5 seconds. Electromyographic activity will also be taken again while the patient is at rest.
- For each subject, the EMG potentials of the analyzed muscles recorded during the maximum voluntary clamping tests will be expressed as a percentage of the average potential recorded during the standardization test (maximum voluntary clamping on cotton rolls).
 - $(\mu V/\mu V \times 100)$.
- To assess muscle symmetry, the EMG waves of the masseter muscles will then be compared by calculating a percent overlap coefficient (POC, %). POC is an index of the symmetrical distribution of muscle activity determined by occlusion. The index ranges from 0% to 100%: a POC of 100% will be achieved when two paired muscles contract with perfect symmetry.

Tinnitus and bruxism will be evaluated by the patient with the VAS score. Tinnitus level will additionally be measured with the Tinnitus Handicap Inventory. Then, an occlusal splint will be prepared for the patients. occlusal splints; will be done with canine-protected occlusion and necessary occlusal arrangements will be made before the plates are delivered to the patients. Splints will be manufactured from hard acrylic and personalized measurements will be taken and the model will be prepared and made. It will be recommended to use them for 24 weeks. Postoperative EMG, Tinnitus Handicap Inventory and VAS scores will be re-evaluated after the use of the occlusal splint.

In the light of the data obtained; Age, gender, disease findings, preoperative and postoperative Tinnitus Handicap Inventory, VAS scores, masseter and temporal muscle strength in EMG will be compared and evaluated.

Inclusion criteria:

Patients older than 18 years

Patients with chronic subjective tinnitus

Patients with Wilkes Stage 1-2

Patients with bruxism

Exclusion criteria:

Patients with Wilkes Stage 3-4-5

Patients with tinnitus due to audiological, neurological, metabolic or pathological reasons

Patients with objective tinnitus

Patients with normal tinnitus

Mentally retarded patients

Hearing loss, use of ototoxic drugs

Those with ear diseases such as acute otitis media, perforated tympanic membrane

Those with Meniere's disease

Patients with middle ear pathology

Those with intracranial pathology

Those with traumatic cervical spine injury

Patients with severe depression diagnosed by a psychologist

Patients who have received TMB treatment in the last two months

Sample Selection: Significance in the G Power analysis program with reference to a previously presented study. When the effect size was taken as 0.08 for the value, it was planned to recruit 70 patients for $\alpha= 0.05$ and 80% power.

Statistical method to be used: All analyzes will be done with SPSS software. In-group temporal evaluations in test and control groups will be evaluated using Pairedsample -T or Wilcoxon test according to normal distribution values. For comparisons between groups, according to the normal distribution of the data, Student-t test will be used for parametric within-group evaluations and Mann Withney U test will be used for non-parametrics. The normal distribution of the data will be evaluated with the Kolmogorov-Smirnov test. The significance value will be taken as 0.05. Relationships between variables will be evaluated with Logistic Regression Analysis or Multivariate Regression Analysis.

Sources List:

1. C.M. DF, M.D.O. M, C.L.P. F, M.A.M. RDS. Otologic symptoms of temporomandibular disorder and effect of orofacial myofunctional therapy. *Cranio - J Craniomandib Pract.* 2008;26(2):118-125.
3. C.M. C, G. F, M.J. T, J.T.T. DS. Clinical evaluation of tinnitus in patients with sleep bruxism: Prevalence and characteristics. *J Oral Rehabil.* 2005;32(11):808-814.
4. S. K, M. K, Y. LB, P. A, S. J. Aural symptoms and signs of temporomandibular disorder in association with treatment need and visits to a physician. *Laryngoscope.* 1999;109(10):1669-1673.
6. AKÇAM ÖU. ORTODONTİDE ELEKTROMİYOGRAFİ. *AÜ Diş Hek Fak Derg.* 2015;42(1):59-67.
7. Tartaglia GM, Moreira Rodrigues da Silva MA, Bottini S, Sforza C FV. Masticatory muscle activity during maximum voluntary clench in different research diagnostic criteria for temporomandibular disorders (RDC/TMD) groups. *Man Ther.* 2008;13(5):434-44

TR

**KÜTAHYA HEALTH SCIENCES UNIVERSITY

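### The between-group test names no baseline adjustment and does not say whether follow-up values or changes are compared, although the groups are formed by diagnosis and each outcome is measured before the splint

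*Combined protocol and SAP*

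**What the plan says.** All references are to the Material-Methods Section.

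- **Groups.** There are two, defined by diagnosis. The first has an intra-articular disorder at Wilkes stage 1 or 2, with no mention of bruxism. The second adds it: "Group II will consist of patients with both Wilkes Stage 1-2 temporomandibular intra-articular disorder and bruxism". No randomisation is described. The splint is prepared for the patients without distinction by group.
- **Measurements.** EMG is recorded before treatment. The VAS scores and the Tinnitus Handicap Inventory (THI) come before the splint is made. Afterwards, "Postoperative EMG, Tinnitus Handicap Inventory and VAS scores will be re-evaluated after the use of the occlusal splint".
- **Within-group tests** (Statistical method to be used). "In-group temporal evaluations in test and control groups will be evaluated using Pairedsample -T or Wilcoxon test according to normal distribution values".
- **Between-group tests** (same paragraph). "For comparisons between groups, according to the normal distribution of the data, Student-t test will be used for parametric within-group evaluations". If normality fails, the fallback is a rank test: "Mann Withney U test will be used for non-parametrics".
- **Regression** (same paragraph). "Relationships between variables will be evaluated with Logistic Regression Analysis or Multivariate Regression Analysis". No outcome, covariate or link to the group comparison is given.

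**The concern.** Patients with and without bruxism have no reason to start at the same level of tinnitus, bruxism or masseter activity. For the bruxism VAS a difference at baseline is expected by design. Neither Student's t nor Mann-Whitney takes a covariate, so any use of the baseline depends on which variable is put into the test, and the plan does not say.

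The wording adds to the doubt. A sentence about comparing groups calls its own test a within-group evaluation, although the sentence before it has already given the within-group tests.

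The contrast matters because the Introduction-Purpose Section sets out to study the TMD and TMD-plus-bruxism groups and to clarify the etiology of subjective tinnitus. A gap that existed before the splint could be reported as evidence that bruxism changes the response to it.

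**Working it through.** **The plan's own figure.** Sample Selection gives 70 patients for an effect size of 0.08, alpha 0.05 and 80% power, without naming the metric or the test. Read as a standardised mean difference between two groups, two-sided, 0.08 needs 2 × (1.960 + 0.842)² / 0.08² ≈ 2,453 per group. The 70 is therefore not reproduced on that reading. Nothing below depends on 0.08; only the total of 70 is used.

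**Inputs.** From the documents: 70 patients, alpha 0.05, two groups, one pre- and one post-splint value per outcome. Assumed, because the documents do not give them: 35 per group, a two-sided test, complete data, SD = 1 at both times, and a pre-post correlation rho of 0.3 to 0.8. The standard error of a difference in follow-up means is √(2/35) = 0.239 SD.

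**Case A: the baseline gap is stable and the groups respond equally.** The same gap appears at follow-up.

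- Follow-up t-test: for a 0.5 SD gap, 0.5/0.239 = 2.09, and the t-test with 68 df rejects in about 54% of trials. For 0.3 SD, 0.3/0.239 = 1.26, and it rejects in about 24%.
- Change-score t-test: the expected difference is 0, so it rejects in about 5%.
- Regression on group and baseline: a bias of gap × (1 − rho) remains. For a 0.5 SD gap this is 0.25 SD at rho 0.5 and 0.15 SD at rho 0.7. By simulation it rejects in about 21% and 13-14%. For a 0.3 SD gap it rejects in 8-11%.

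**Case B: the gap shrinks toward the mean, with no group effect once baseline is accounted for.** For a 0.5 SD baseline gap, the expected follow-up difference is 0.5 × rho and the expected difference in change is −0.5 × (1 − rho). The standard error of the change difference is 0.239 × √(2(1 − rho)). Rejection rates use the normal approximation.

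| rho | Follow-up bias (SD) | Bias/SE | Rejects | Change bias (SD) | Bias/SE | Rejects |
|---|---|---|---|---|---|---|
| 0.3 | 0.15 | 0.63 | 10% | −0.35 | 0.35/0.283 = 1.24 | 24% |
| 0.5 | 0.25 | 1.05 | 18% | −0.25 | 0.25/0.239 = 1.05 | 18% |
| 0.7 | 0.35 | 1.46 | 31% | −0.15 | 0.15/0.185 = 0.81 | 13% |

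Here the regression is the unbiased analysis and rejects in about 5%.

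The follow-up-only test is biased in both cases. Change scores are right in case A and the regression is right in case B. The data will not show clearly which case applies.

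**Precision with no baseline gap.** The outcome variances are 1 (follow-up), 2(1 − rho) (change) and 1 − rho² (regression). With 35 per group, the difference detectable with 80% power is 0.679 times the square root of each, in SD:

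| rho | Follow-up | Change | Regression |
|---|---|---|---|
| 0.3 | 0.68 | 0.80 | 0.65 |
| 0.5 | 0.68 | 0.68 | 0.59 |
| 0.7 | 0.68 | 0.53 | 0.49 |
| 0.8 | 0.68 | 0.43 | 0.41 |

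For a true difference of 0.5 SD, the follow-up test has about 55% power. The regression alone has about 66% at rho 0.5 and 81% at rho 0.7. A rule that both baseline-aware analyses must be significant has about 49% and 73%.

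**The case against.** - **The plan does not say that follow-up values are tested.** A t-test on changes fits the same sentence, and the Material-Methods Section elsewhere says that pre- and postoperative values will be compared. A reader might infer that a 54% false-positive rate is built into the plan. The documents do not support that. The rate holds only on the follow-up-only reading with a stable gap. What stands is that the plan leaves that reading open.
- **The contrast is not a treatment contrast.** A reader might infer that baseline gaps could pass for treatment effects, the more so because the methods paragraph speaks of test and control groups. No group without a splint is described. The contrast is bruxism status. The stated hypothesis concerns a fall in levels after the splint, which the paired tests address using each patient's own baseline. This objection stands and limits the importance of the point.
- **The regression sentence might already cover adjustment.** It could house such a model, but without an outcome, covariates or a link to the groups it is not a planned adjusted comparison.
- **Baseline-adjusted regression is no cure.** In case A it rejects up to about four times as often as it should (21% against 5%). It does not remove confounding between groups formed by diagnosis. This stands, and it is why the regression should not simply be named the primary analysis.

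**Conclusion.** The point holds in a limited form. The between-group analysis is underspecified, has no stated baseline adjustment, and is applied to groups formed by diagnosis although the baseline values are collected. On the follow-up-only reading, a 0.5 SD gap with no difference in response gives a significant result in about 54% of trials if the gap is stable, and in 10-31% if it shrinks toward the mean (rho 0.3-0.7). Change scores give about 5% in the stable case. These figures rest on the assumed equal groups of 35, the assumed correlations and the assumed size of gap.

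The documents do not support three stronger conclusions: that the plan commits to follow-up values, that the test of the splint hypothesis is compromised, or that covariance adjustment alone would put the comparison right. The change is worth making before analysis because the between-group contrast serves a stated aim of the study. It does not call the pre-post tests into question.

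**What to change.** Replace the between-group sentence with wording to this effect:

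- Differences between groups in response to the splint will not be claimed from follow-up scores alone.
- For THI, VAS and EMG, two baseline-aware comparisons will be reported: (a) the difference between groups in change from baseline; (b) a regression of the follow-up value on group and the baseline value of the same outcome, with age, sex and Wilkes stage (1 or 2) as covariates.
- Both estimates will be given with confidence intervals. The group term will be read as an association because the groups are not randomised. Disagreement between the two will be reported as uncertainty.

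Delete the words within-group from this sentence. Replace test and control groups with the names of the two diagnostic groups. The Inclusion criteria list bruxism, which conflicts with a Group I defined without it; those passages must be reconciled so that the contrast is defined.

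**Cost.** Only statistical wording changes. The baseline values, age, sex and Wilkes stage are already collected, and SPSS fits the model. The two analyses rest on different assumptions and may disagree when baselines differ. Requiring both to be significant would cost power (about 49% at rho 0.5 and 73% at rho 0.7 for a 0.5 SD difference, against about 55% for the follow-up test), so no gain in power should be claimed for such a rule.

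### A normality pre-test on unspecified data picks the test for each outcome; separately, neither between-group test offered allows for unequal spread

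*Combined protocol and SAP*

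**What the plan says.** The rule is in the Material-Methods Section, under Statistical method to be used. Within groups: "In-group temporal evaluations in test and control groups will be evaluated using Pairedsample -T or Wilcoxon test according to normal distribution values". Between groups: "Student-t test will be used for parametric within-group evaluations and Mann Withney U test will be used for non-parametrics". That second sentence opens as a between-group rule but labels the Student-t comparison as within-group, so its wording is inconsistent. The choice in both cases rests on one further sentence: "The normal distribution of the data will be evaluated with the Kolmogorov-Smirnov test". On the level: "The significance value will be taken as 0.05".

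The plan does not state the variable checked (raw score, change or residual), whether groups are checked separately or pooled, the level of the check, whether the Lilliefors correction is used, or what happens if groups or time points disagree. It names no unequal-variance test.

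The groups are formed by diagnosis, not by randomisation. Group I has the joint disorder only, and "Group II will consist of patients with both Wilkes Stage 1-2 temporomandibular intra-articular disorder and bruxism". The total is 70 patients; no group sizes or ratio are given.

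**The concern.** Nobody can tell from the text which test a given outcome will receive, because the choice waits for the data. A paired t-test depends on the distribution of within-patient differences. Skewed scores can have near-normal differences, and the reverse, so a check on raw scores may look at the wrong quantity. If the check is run per group, Group I and Group II may be reported with a mean-based test and a rank test for the same outcome, and the two results cannot be set side by side.

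A second weakness does not depend on the pre-test. Student-t in its usual form pools the variances. Mann-Whitney, when read as a comparison of means, needs the two distributions to have the same shape and spread. Groups formed on bruxism, in no fixed ratio, may differ in spread. If they do, the actual error rate of the between-group comparison can move away from the stated 0.05.

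**Working it through.** **The plan's own figures.** The plan states no error rate for the two-stage rule, so there is none to reproduce. From Sample Selection only the total of 70 and alpha of 0.05 are used here. The 70 does not follow from the stated effect size of 0.08: read as a standardised difference between two groups, n per group = 2 × (1.960 + 0.842)² / 0.08² ≈ 2,453. That is a separate matter and does not affect this point.

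**Assumed inputs.** The documents give none of the following.
- Splits of 35:35, 50:20 and 45:25.
- SD ratios of 0.5, 1, 1.5 and 2.
- Normal, gamma (shape 2, skewness 2/√2 = 1.4; shape 4, skewness 1.0) and lognormal (log-SD 0.6) data.
- Two-sided 0.05, with the normality check at 0.05 in each group.

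**Step 1: different within-group tests for one outcome.** If each group is checked separately and fails with probability p, the groups disagree with probability 2p(1 − p). With the Lilliefors version at n = 35:
- gamma (shape 4), p = 0.29: 2 × 0.29 × 0.71 = 0.41
- gamma (shape 2), p = 0.52: 2 × 0.52 × 0.48 = 0.50
- whole-number VAS (mean 5, SD 2), p = 0.55: 2 × 0.55 × 0.45 = 0.50

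Direct simulation at 35:35 gives 10% (normal), 50% (gamma, shape 2) and 42% (lognormal). Without the correction these become 0%, 7% and 20%.

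**Step 2: within-group error rate.** With the pre-test applied to differences (n = 35, 8,000 runs), the two-stage rule rejects a true null in 4.8–5.0% of runs for normal, heavy-tailed, whole-number and skewed-score pairs.

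**Step 3: between-group error rate.** True means are equal, with 40,000 runs per setting. The rule modelled is Student-t if both groups pass the Lilliefors check, otherwise Mann-Whitney. The SD ratio is second group to first; at 50:20 the second group is the smaller. Entries are the percentage rejected. The Monte Carlo standard error is √(0.05 × 0.95 / 40,000) ≈ 0.1 percentage points at 5%, and 0.2 at 20%.

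| Data | Split | SD ratio | Two-stage | Student-t alone | Mann-Whitney alone | Welch |
|---|---|---|---|---|---|---|
| Normal | 35:35 | 1 | 5.1 | 5.0 | 4.9 | 5.0 |
| Normal | 35:35 | 2 | 5.4 | 5.1 | 5.7 | 4.9 |
| Normal | 50:20 | 1 | 5.3 | 5.2 | 5.0 | 5.1 |
| Normal | 50:20 | 1.5 | 9.7 | 9.7 | 7.3 | 5.0 |
| Normal | 50:20 | 2 | 13.4 | 13.5 | 9.3 | 5.1 |
| Normal | 50:20 | 0.5 | 1.4 | 1.2 | 2.5 | 5.0 |
| Gamma (shape 2) | 35:35 | 1 | 5.3 | 4.9 | 4.9 | 4.9 |
| Gamma (shape 2) | 35:35 | 1.5 | 9.7 | 5.3 | 10.0 | 5.2 |
| Gamma (shape 2) | 35:35 | 2 | 15.6 | 5.7 | 16.4 | 5.6 |
| Gamma (shape 2) | 50:20 | 1.5 | 12.3 | 9.7 | 11.9 | 5.9 |
| Gamma (shape 2) | 50:20 | 2 | 18.6 | 13.9 | 18.2 | 6.5 |
| Gamma (shape 2) | 50:20 | 0.5 | 8.7 | 1.6 | 9.4 | 5.0 |
| Lognormal | 35:35 | 2 | 20.7 | 5.8 | 21.2 | 5.6 |
| Lognormal | 50:20 | 2 | 22.2 | 13.8 | 22.2 | 7.2 |

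At 45:25 with the smaller group 1.5 times more variable, the two-stage rule gives 8.2% (normal) and 11.9% (gamma), against 5.1% and 5.8% for Welch. Separate runs of the normal 50:20, ratio 2 setting gave 13.3–14.1%. With uncorrected Kolmogorov-Smirnov, the gamma figures at ratio 2 fall to 7.2% (35:35) and 14.7% (50:20), because Student-t is kept more often.

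**Reading the table.** With equal spread, the two-stage rule holds its level. Where it does not, it follows whichever branch it mostly uses: Student-t for normal data with unequal sizes, Mann-Whitney for skewed data.

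**The case against.** The strongest reply is that the pre-test causes none of the error-rate trouble. A reader might infer that choosing the test by a normality check inflates the error rate. The table does not support that: at equal spread the rule gives 5.1–5.4%, and for normal data at 50:20 with ratio 2 it gives 13.4% against 13.5% for Student-t alone. Removing the check without changing the tests would cure nothing there. This stands, and it is why the two defects are kept apart.

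The trial's hypothesis is a before-after effect of the splint, and the simulated within-group rule kept its level. This also stands: the point is no evidence against the test of the main hypothesis.

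The settings are assumptions. Normal data in equal groups show no material problem even at twice the spread, and the error can be conservative. The case for unequal spread is most concrete for the bruxism VAS, but the groups are defined by bruxism, so equal mean scores there are hardly a meaningful null. For tinnitus VAS, the Tinnitus Handicap Inventory and EMG, unequal spread is possible but not shown.

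Two skewed distributions with equal means and different spreads do differ, so part of the Mann-Whitney excess is correct detection of a difference in distribution. It counts as error only if the result is reported as a difference in means.

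Finally, the wording does not exclude a check on differences, nor a Student-t with an unequal-variance option. That is so, but the plan does not state either, and stating them is the remedy.

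**Conclusion.** The point holds as two separate, low-priority defects of specification.

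1. The pre-test leaves the method for each outcome open until the data are seen, and does not name the quantity checked. Different within-group tests in the two groups are possible only if normality is checked per group. The 40–50% frequency needs the Lilliefors version and skewed or whole-number data; without the correction the simulated range is 0–20%. The between-group comparison uses one test and is untouched by this.

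2. Neither between-group option protects against unequal spread. The actual error rate is about 5% when spreads are equal, or when data are normal and groups equal. For normal data it is 8–14% if the smaller group is 1.5–2 times more variable, and about 1.5% if the larger group has twice the spread. For gamma data, with the 1.5–2 times larger spread in one of two equal groups or in the smaller group, it is roughly 10–19% with the Lilliefors version. Lognormal data reach 22%. Welch's test stays between 4.5% and 7.2% in the settings run.

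The documents do not support the stronger conclusion that the trial's error rate is inflated. Group sizes, SD ratios, distribution shapes, per-group checking and the Lilliefors correction are all assumptions, and the direction of the error depends on them.

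**What to change.** Delete the normality rule and name one method per outcome, the same in both groups.
- **Within groups:** paired t-test on the 24-week minus baseline differences, with a 95% confidence interval.
- **Between groups:** Welch's t-test on the change, or a baseline-adjusted regression with heteroscedasticity-robust standard errors. Correct the sentence that labels the between-group test as within-group.
- **Sensitivity:** report Wilcoxon and Mann-Whitney for every outcome, not only where a check fails. Describe Mann-Whitney as a comparison of distributions. Inspect differences or residuals by plot, without letting the plot change the main method.

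The change is to wording only: no added patients, visits or measurements. The price is a slight loss of efficiency for strongly skewed outcomes, which the rank analyses cover. Welch is not exact either: it reached 7.2% for lognormal data at 50:20, against 22.2% for the planned rule.
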